Methodology / Design	
Non-randomised open label diagnostic study
 
We are planning to record 250 pre-defined abnormal ECGs (50 each of atrial fibrillation, atrial flutter, pre-excitation, ventricular tachycardia, , supraventricular tachycardia) and 150 control ECGs (100 sinus rhythm, 50 sinus tachycardia) using both the AliveCor Smartphone device and a 12-lead ECG. All 400 ECGs will then be read by 3 blinded reporters – a Consultant Electrophysiologist, a Consultant General Cardiologist and a General Practitioner. The output of the AliveCor automatic detection algorithm will also be recorded as a fourth reporter. The screening characteristics of all 4 reporters using the AliveCor device vs the definitive 12 lead ECG will be analysed and compared.
 
Patients can be recruited from different cardiology clinics; at the end of an exercise test to record sinus tachycardia, and in the catheter lab during electrophysiological studies/ ablation procedures to record arrhythmias.
 
Every patient will be counselled about the project by a member of the cardiology / research team (doctor or qualified research nurse) and will be provided with a patient information sheet. Patients will be given up to 2 weeks to consider participation in the study. If in agreement, written informed consent will be obtained.
 
A 30-second ECG tracing will be obtained by simply holding the Smartphone and placing at least 1 finger from each hand on electrodes embedded into the back of the Smartphone case (figure 2). For sedated patients in the catheter lab, AliveCor electrodes will be placed and taped on patient chest wall, left parasternal third intercostal space. The AliveCor ECG tracing will be recorded as close to simultaneously as the 12 lead ECG

	recording as possible.
Duration	2 years
Participating Centres	Blackpool Victoria Hospital
Primary End Point	Screening characteristics and diagnostic accuracy of AliveCor ECG recordings to detect cardiac arrhythmias
Number of participants	400
Main Inclusion /Exclusion Criteria	
Inclusion:
 
 • Male or female patients >18 years with 12 lead ECG finding of arrhythmia, manifest pre-excitation, pacing rhythm, sinus rhythm or sinus tachycardia. 
Exclusion Criteria:
 
 • Patients <18 years of age. • Patients unable to or unwilling to use the device.

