Statistical Methodology and Analysis	
400 patients are planned to be recruited as follows:
 
50 patients with supraventricular tachycardia (SVT) 50 patients with atrial flutter (AFl) 50 patients with atrial fibrillation (AF) 50 patients with ventricular tachycardia (VT) 50 patients with manifest pre-excitation 50 patients with sinus tachycardia to constitute the tachycardia control group
 
100 normal ECGs will also be collected from the first 100 patients who have regular sinus rhythm to constitute the sinus rhythm control group.
 
ECGs will be recorded in duplicate, with one recording being made using the AliveCor device, and one recording being made using a normal 12-lead ECG. Recordings will be undertaken as close to simultaneously as possible. The ECG diagnosis will be made by the lead Electrophysiologist on the 12-lead ECG so produced and this will be taken as the correct ECG diagnosis.
 
All ECGs (both 12-lead and AliveCor) will be reported by a Consultant Electrophysiologist, a General Cardiologist and a General Practitioner, blinded to the full study protocol and the patient allocation group. The output of the AliveCor algorithm for automatic ECG diagnosis will also be recorded. The readers will firstly read the AliveCor ECGs and at a later date read the 12-lead ECGs to prevent comparisons between the ECGs and to give accurate screening characteristics for AliveCor ECGs.
 
The diagnostic accuracy and screening characteristics of ECGs generated by the AliveCor device will be reported for each arrhythmia individually and in combination both by each reporter. To calculate screening characteristics, ECGs of sinus rhythm and sinus tachycardia will also be included in each analysis as normal controls. 95% confidence intervals will be calculated.
 
The primary end-point will be the sensitivity and screening characteristics of detecting each arrhythmia individually and in combination by each reporter using the AliveCor device, calculating 95% confidence intervals.
 
The binomial exact calculation would be used to calculate confidence intervals.
 
With a sample size of 50 patients with one arrhythmia, a sensitivity of 80% would produce a 95% confidence interval of 68.9% to 91.1%. With a sample size of 250 (all arrhythmias combined), a sensitivity of 70% would produce a 95% confidence interval of 64.5% to 75.1%, i.e. an absolute error of $\pm 5\%$.
 
The main secondary end-point will be to compare the sensitivity of a

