
	
Consultant Electrophysiologist in detecting all arrhythmias using the AliveCor device vs the originally coded 12-lead ECG, to test whether the AliveCor device is non-inferior to the original 12-lead ECG diagnosis. Assuming a 95% one-sided confidence interval and a power of 80%, if there is a true difference in sensitivity in favour of the 12-lead ECG over an AliveCor ECG of 10%, and then a sample size of 301 would be needed to exclude a difference in favour of the 12-lead ECG of more than 16%.
 
Further secondary end-points will be to compare a Consultant Electrophysiologist with a General Consultant Cardiologist with a General Practitioner and with the automated AliveCor ECG diagnosis using their automatic algorithm.

--	----------------------------------------------------------------------------------------------------------------------------------------------------------------------------------------------------------------------------------------------------------------------------------------------------------------------------------------------------------------------------------------------------------------------------------------------------------------------------------------------------------------------------------------------------------------------------------------------------------------------------------------------------------------------------------------------------------------------------------------------------------------------------

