6.1 Sample Size Determination

With a sample size of 50 patients with one arrhythmia, a sensitivity of 80% would produce a 95% confidence interval of 68.9% to 91.1%. With a sample size of 250 (all arrhythmias combined), a sensitivity of 70% would produce a 95% confidence interval of 64.5% to 75.1%, i.e. an absolute error of $\pm 5\%$.

The main secondary end-point will be to compare the sensitivity of a Consultant Electrophysiologist in detecting all arrhythmias using the AliveCor device *vs* the originally coded 12-lead ECG, to test whether the AliveCor device is non-inferior to the original 12-lead ECG diagnosis. Assuming a 95% one-sided confidence interval and a power of 80%, if there is a true difference in sensitivity in favour of the 12-lead ECG over an AliveCor ECG of 10%, and then a sample size of 301 arrhythmias would be needed to exclude a difference in favour of the 12-lead ECG of more than 16%.

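### Section 6.1 calls for 301 arrhythmias where 250 are planned, and neither printed precision interval is the exact binomial interval at its stated sample size

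*Combined protocol and SAP*

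**What the plan says.** **Planned cases.** The synopsis (section 1, Methodology / Design) states: "We are planning to record 250 pre-defined abnormal ECGs". The groups are AF, atrial flutter, pre-excitation, VT and SVT, 50 each, with 150 sinus recordings (100 sinus rhythm, 50 sinus tachycardia) to make 400. The role of the sinus recordings is given in the synopsis statistical row: "ECGs of sinus rhythm and sinus tachycardia will also be included in each analysis as normal controls".

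**Precision, primary endpoint.** Section 6.1: "With a sample size of 50 patients with one arrhythmia, a sensitivity of 80% would produce a 95% confidence interval of 68.9% to 91.1" (per cent), and "With a sample size of 250 (all arrhythmias combined), a sensitivity of 70% would produce a 95% confidence interval of 64.5% to 75.1" (per cent), the latter summarised as an absolute error of ±5%. The synopsis repeats both. The synopsis and section 6.2 both specify the exact binomial method for confidence intervals.

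**Size, main secondary endpoint.** Section 6.1 assumes a one-sided 95% interval, 80% power and a true 10-point deficit in sensitivity, and says "a sample size of 301 arrhythmias would be needed to exclude a difference in favour of the 12-lead ECG of more than 16" points. The synopsis gives the same number without its unit: "then a sample size of 301 would be needed to exclude a difference in favour of the 12-lead ECG of more than 16" points.

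**Comparator.** In 6.1 it is "the originally coded 12-lead ECG, to test whether the AliveCor device is non-inferior to the original 12-lead ECG diagnosis", and the synopsis agrees. The synopsis also makes the lead electrophysiologist's 12-lead diagnosis the correct answer. Sections 2.2 and 6.2 speak more loosely of the 12-lead ECG, and the synopsis schedules later blinded readings of the 12-lead traces.

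**The concern.** Section 6.1 uses 250 for all arrhythmias combined in one paragraph and requires 301 in the next. Nothing in the documents bridges the two or accepts a lower power. The total of 400 does not help, because 6.1 counts arrhythmias and sensitivity is estimated in arrhythmia recordings only.

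The two precision statements look wrong for different reasons: one appears to carry the wrong sample size, the other the wrong method.

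At stake is the stated sample-size basis of the primary and main secondary endpoints. If non-inferiority is not shown, a reader who sees 250 against a stated need of 301 cannot tell whether the study was too small or the device was too insensitive. A reader of the precision statements would also expect tighter lower bounds than the planned analysis can give.

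**Working it through.** **1. The 301.** From 6.1: one-sided alpha 0.05 (z = 1.6449), power 80% (z = 0.8416), true difference 0.10, margin 0.16, so the distance to the margin is 0.06. The two sensitivities are not given. Assuming 95% for the 12-lead ECG and 85% for AliveCor, the unpaired formula gives

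n = (1.6449 + 0.8416)² × (0.95×0.05 + 0.85×0.15) / 0.06² = 6.183 × 0.175 / 0.0036 = 300.5, i.e. 301.

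Other pairs 10 points apart do not fit: 90% v 80% gives 430, and 100% v 90% gives 155. The shortfall is 301 − 250 = 51 cases (17%). Under this same formula, power at 250 is Φ(0.06/√(0.175/250) − 1.6449) = Φ(0.623) = 73%.

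**2. Interval for 70% at n=250.**

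| Method | Case | 95% interval |
|---|---|---|
| Printed | n=250 | 64.5% to 75.1% |
| Exact (Clopper-Pearson) | 175/250 | 63.91% to 75.61% |
| Wald | 175/250 | 64.32% to 75.68% |
| Wilson | 175/250 | 64.05% to 75.34% |
| Jeffreys | 175/250 | 64.11% to 75.43% |
| Exact | 210/300 | 64.47% to 75.13% |

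None of these methods gives the printed interval at n=250. The exact method at 210/300 does. The half-widths at 250 are −6.1/+5.6 points, not ±5.

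**3. Interval for 80% at n=50.** Wald: 0.80 ± 1.96 × √(0.8×0.2/50) = 0.80 ± 0.111, i.e. 68.9% to 91.1%, as printed. Exact at 40/50: 66.28% to 89.97%, i.e. −13.7/+10.0 points. The printed lower bound is 2.6 points too high, against 0.6 points for the combined figure.

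**4. Power at 250, by comparator.**

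*Coded 12-lead diagnosis.* This is the reference standard, so its sensitivity is 100% by definition. A true 10-point difference means AliveCor sensitivity 90%, and the margin means testing against 84%. The one-sided 5% exact test needs at least 220/250 (actual alpha 0.0468; one-sided lower bound 84.1% at 220, 83.6% at 219). Power is 87.5% exact. The normal approximation, Φ(0.06/√(0.09/250) − 1.6449), gives 93.5%.

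*Separate 12-lead reading.* The comparison is paired, with variance (ψ − 0.10²)/n, where ψ is the discordance. At assumed sensitivities of 95% v 85%, ψ lies between 0.10 (every discordant pair favours the 12-lead) and 0.05 + 0.15 = 0.20 (misses never coincide). By normal approximation:

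| Assumed ψ | Power at 250 | n for 80% |
|---|---|---|
| 0.10 | about 94% | 155 |
| 0.15 | 81% | 241 |
| 0.185 | 73% | 301 |
| 0.20 | 70% | 327 |

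The value 0.185 is what independent readings would give (0.95×0.15 + 0.05×0.85), which is why it returns 301 as well. Power is 80% at 250 when ψ is about 0.156.

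**The case against.** The strongest reply is that nothing is lost in practice. On the comparator wording in 6.1 and the synopsis, 250 cases give more than 80% power. On a separate reading, near-simultaneous traces from the same patient may well agree more than independent ones, which would raise power above the unpaired 73%. The precision figures are illustrations at assumed sensitivities. The exact method is already fixed for the analysis, so reported intervals would be correct whatever 6.1 prints, and no decision rule rests on them.

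Most of this stands, and it limits the consequence. A reader might infer from 301 against 250 that the non-inferiority comparison is underpowered. The documents do not support that: they give neither the two sensitivities nor the discordance, and the plausible range runs from well above 80% to about 70%. The reply does not rescue the sentence itself. If 250 is enough, the statement that 301 are needed is wrong; if 301 is right, the plan does not meet it.

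A reader might also infer, from the match with 300 and from paced rhythm in the primary objective (2.2) and the synopsis inclusion criteria, that the case total is still open or that a sixth group was dropped. The synopsis fixes the total at five groups of 50, and 4.1.2 excludes patients with pacemakers. The origin of the 300 is not documented. The paced-rhythm wording is a separate inconsistency.

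**Conclusion.** Three figures in 6.1, repeated in the synopsis, are wrong as written. The stated need of 301 arrhythmias exceeds the planned 250 by 51. The n=250 interval should be 63.9% to 75.6%, and the n=50 interval 66.3% to 90.0%. These conclusions need no outside assumption: they follow from the plan's own counts and its own interval method.

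An actual loss of power is possible but not shown. The power figures rest on assumptions: 90% true sensitivity against a fixed reference, or 95% v 85% with ψ from 0.10 to 0.20. The choice between the two comparators is an ambiguity in the plan, not a contradiction.

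A reader might extend the argument to the per-arrhythmia non-inferiority assessments in 6.2, with 50 cases each. The plan states the 16-point margin and 10-point difference only for all arrhythmias combined, so any power figure at n=50 would borrow them.

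**What to change.** In section 6.1 and the synopsis:

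1. Print the exact intervals: 40/50 gives 66.3% to 90.0%; 175/250 gives 63.9% to 75.6%. Replace ±5% with −6.1/+5.6 points.
2. Name one comparator, either the originally coded 12-lead diagnosis or the separate blinded 12-lead reading, and use the same wording in 2.2, 6.1 and 6.2.
3. Replace the 301 sentence with the power at 250, its assumptions and the method used.
   - *Coded diagnosis:* true sensitivity 90%, one-sided 5% exact test against 84%, met at 220/250 or more, power 87.5% (93.5% by normal approximation).
   - *Separate reading:* assumed sensitivities and discordance, with the corresponding paired power (about 94%, 81%, 73% or 70% at 0.10, 0.15, 0.185 or 0.20 for 95% v 85%, normal approximation).
   - *If the unpaired formula is kept:* state that it assumes 95% v 85% and gives 73% at 250.
4. Optional: if per-arrhythmia power at n=50 is reported, label the margin and the true difference as assumed.

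Separately, reconcile the paced-rhythm wording in 2.2 and the synopsis inclusion criteria with the exclusion in 4.1.2.

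The cost is protocol wording and one recalculation, with no extra patients if 250 and its power are accepted. The stated precision becomes slightly wider, the stated power may fall below 80%, and the team must commit to one comparator.

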6.2 Statistical Methods

The diagnostic sensitivity, screening characteristics and accuracy of the AliveCor device will be reported for each arrhythmia individually and for all arrhythmias combined, measuring 95% confidence intervals using the binomial exact method.

Non-inferiority will be assessed for each arrhythmia individually, and all arrhythmias combined for a Consultant Electrophysiologist reading the AliveCor generated ECG *vs* a near-simultaneously recorded 12-lead ECG.

The Chi-squared test and Fisher's exact test will be used to compare proportions. The McNemar test will be used to compare paired dichotomous dependent variables.

6.3 Interim Analyses

No interim follow-up is planned as this is a diagnostic study. There is no therapeutic intervention in this study. However, the Principal Investigator will be closely monitoring this study and its progression.

7 Safety and Adverse Events

A search of the Medicines and Healthcare Products Regulatory Agency website revealed no Manufacturer Field Safety Notices or Medical Device Alerts for this device. No reports of adverse events were identified from a search of the US Food and Drug Administration (FDA)

database: Manufacturer and User Device Facility Experience (MAUDE).¹⁰ No drug or intervention in this study. All Adverse Events (AE) will be recorded according to the R&D Office Procedure and the Trust Policy on Incident Reporting.

7.1 Recording of Adverse Events

All Adverse Events (AE) Serious Adverse Events (SAE) will be recorded according to the R&D Office Procedure and the Trust Policy on Incident Reporting.

All adverse events occurring during the study period will be recorded. The clinical course of each event will be followed until resolution, stabilisation, or until it has been determined that the study treatment or participation is not the cause. Serious adverse events that are still ongoing at the end of the study period will be followed up to determine the final outcome.

8 Data Handling and Record Keeping

8.1 Confidentiality

Information about study participants will be kept confidential and managed according to the requirements of the Data Protection Act and the UK Policy Framework for Health and Social Care Research

The identifiable details (Hospital number and date of birth) will be collected from participants in this study.

Principal Investigator will have access to this information

Data will be anonymised if placed on a computer database. Patient will be given a study ID (AliveCor 001, AliveCor 002, etc.) as per order of recruitment.

The Principal Investigator is the custodian of the data.

8.2 Case Report Forms

The study case report form (CRF) is the primary data collection instrument.

- All data requested on the CRF/DCF will be recorded.
- All missing data must be explained. If a space on the CRF/DCF is left blank because the procedure was not done, or the question was not asked, we will write “N/D”.
- If the item is not applicable to the individual case, we will write “N/A”.
- All entries should be printed legibly in black ink.
- To correct any data entry error, will draw a single straight line through the incorrect entry and enter the correct data above it. All such changes must be initialled and dated.

8.3 Records Retention

Period of record retention will be 5 years

Filing arrangements for the CRFs and consent forms will be kept in research office in Lancashire Cardiac Centre, Blackpool Victoria Hospital. Records will also be archived in line with R&D Standard Operating Procedures (SOP).

9 Study Monitoring, Auditing, and Inspecting

The investigator will permit study-related monitoring, audits and inspections by the Ethics Committee, the Sponsor and the Research Governance Manager.

Participation as an investigator in this study implies adherence to the principles and responsibilities of the UK Policy Framework for Health and Social Care Research, ICH/GCP and Directive 2000/20/EC.

10 Ethical Considerations

Informed consent will be obtained from each participant as detailed in the consent section. Data protection will be ensured throughout the study. The data will be anonymous and information governance guidelines will be religiously followed to ensure confidentiality. No added potential harm could be caused to any participant from the use of the AliveCor device. The study will not be funded by any company with an interest into their desired outcome. Investigators participating in the study must declare no conflict of interest.

This study will be conducted according to the standards of International Conference on Harmonization, Good Clinical Practice Guideline, Health Research Authority regulations, any applicable government regulations, Trust and Research Office policies and procedures.

This protocol and any amendments will be submitted to the Health Research Authority for review and approval of the study conduct.

No research studies can commence until the principal investigator has received a letter Confirming Capability and Capacity from the Trust issued by the Research and Development Office and a letter of approval from the Health Research Authority and REC.

